1.4 DOSE RATIONALE

Data supports that carfilzomib as a single agent can produce substantial response rates in myeloma subjects across a variety of dosing cohorts. Responses were seen over a wide therapeutic window, from 15 to 27 mg/m². Maximum proteasome inhibition was seen at doses 11 mg/m² and higher in whole blood samples taken 1 hour after the first dose. The final analysis of the human pharmacokinetic (PK) data i shows rapid and similar to the results from the animal studies. Carfilzomib is rapidly cleared from plasma with an elimination half-life of < 60 minutes at the 20 mg/m² dose. Large, single arm studies of the 27 mg/m² dose are ongoing and suggest that this dose is very well tolerated with subjects being treated for >10 cycles without cumulative toxicities.

By the end of 2009, 269 subjects with relapsed and refractory multiple myeloma have been enrolled in the PX-171-003-A1 study. The goal of dose escalating to 27 mg/m² beginning with Cycle 2 is to improve ORR, DOR, and TTP.

Safety and efficacy results are available for 2 completed phase 3 studies, PX-171-009 (ASPIRE) and Study PX-171-011 (FOCUS). FOCUS was an open-label phase 3 study of carfilzomib versus a combination of corticosteroids and cyclophosphamide as supportive care. Carfilzomib as a single agent was well tolerated at a dose 20 mg/m² and 27 mg/m² in cycles 10 and higher. The study did not show superiority of carfilzomib over supportive care in overall survival; however, carfilzomib as monotherapy did show a higher overall response rate as compared to that of supportive care. Results from phase 3 study ASPIRE comparing carfilzomib, lenalidomide, and dexamethasone (CRd) versus lenalidomide and dexamethasone (Rd) in subjects with relapsed multiple myeloma showed that patients in the CRd arm showed significantly longer rates of progression free survival. Stepped up dosing of 20/27 mg/m² during cycles 1-12 and 27 mg/m² was well tolerated with improvement in overall quality of life reported. Three other phase 3 studies 2011-003 (ENDEAVOR), 2015-005 (CLARION), and CFZ014 (A.R.R.0.W.) remain ongoing with very good responses reported.

In multiple preclinical studies, the tolerability of carfilzomib in rats has been shown to be significantly higher when administered as a 30 minute infusion as compared to a rapid IV bolus. Toxicities observed with IV bolus injection of carfilzomib *above the MTD* at a dose of 48 mg/m² include evidence of prerenal azotemia (transient increases in BUN > creatinine) as well as lethargy, piloerection, dyspnea, and gastrointestinal bleeding. Notably, death occurred in ~50% of animals at 48 mg/m² when carfilzomib was given as a bolus. Administration of the same dose (48 mg/m²) as a 30 minute continuous infusion was well tolerated, with no changes in BUN and

creatinine and substantially reduced signs of lethargy, piloerection, or dyspnea. Moreover, all animals in the infusion treatment groups survived. The only toxicity observed following infusion of carfilzomib for 30 minute was gastrointestinal bleeding. The reduced toxicity seen with dosing by infusion may reflect the reduced C_{max} of carfilzomib vs that with bolus dosing. Inhibition of the pharmacological target of carfilzomib (the chymotrypsin-like activity of the proteasome) was equivalent in the bolus and infusion treatment groups.

In the clinic, the MTD in the multiple myeloma (MM) setting when administered as a 30 minute infusion has been determined to be 20/56 mg/m2. Twenty-seven mg/m2 of carfilzomib (bolus administration over 2-10 minutes) is well tolerated in MM subjects overall and can be tolerated for >12 cycles in late stage MM subjects with substantial comorbidities.

A phase 1b/2 dose escalation study (PX-171-007) of single agent carfilzomib administered was completed and as of 19 July 2011, 65 subjects with solid tumors received treatment in the l Phase 2 portion of the study at the 20/36 mg/m² MTD established in the phase 1b portion (bolus administration over 2-10'). A review of the tolerability of 36 mg/m² carfilzomib in these subjects indicates that this regimen was very well tolerated with only one DLT (fatigue) and an overall adverse event profile similar to that seen with the 27mg/m^2 carfilzomib experience with bolus dosing (see IB for details). Three subjects completed > 12 cycles of therapy at 36 mg/m² with no evidence of cumulative toxicity. There were no significant DLTs observed; the majority of discontinuations on the study were due to progressive disease. Because of the long-term tolerability of carfilzomib, the Phase 1b portion of this study was reopened, and a separate arm for multiple myeloma was added.

In the PX-171-007 trial, more recently subjects have been treated with carfilzomib given as a 30minute infusion in order to potentially minimize Cmax-related infusion events. The protocol was amended and doses of 20/36 (20 mg/m² given on Days 1 and 2 of cycle 1 only; followed by 36 mg/m² for all subsequent doses), 20/45, 20/56 mg/m2 and so forth are being investigated. Doses of 20/56 mg/m2 are currently being given in two separate cohorts of subjects with advanced MM and advanced solid tumors; the lower doses were well tolerated. Preliminary tolerability information at this dose level (20/56 mg/m²) indicated that it is reasonably well tolerated, with minimal infusion reactions. In some cases at 20/56mg/m², dexamethasone was increased from 4mg/dose to 8mg with the 56mg/m² doses in order to reduce fevers and hypotension. As of March 20, 2010, seven subjects have received 20/56mg/m² and are tolerating it. Subjects with advanced, refractory MM being treated at 36mg/m² and 45mg/m² have shown very good tolerability (>6 months in some cases) with documented minimal and partial responses in these heavily pretreated subjects. These data indicate that carfilzomib 30-minute infusion can be given at very high levels, with >95% inhibition of blood proteasome levels achievable and with (at least) acute tolerability. All protocols using $\geq 36 \text{mg/m}^2$ carfilzomib are now administering the drug as a 30-minute infusion.

In addition to the above observations, a phase I study of carfilzomib in subjects with relapsed and refractory multiple myeloma was reported in abstract form at the 2009 American Society of Hematology meeting which demonstrated that carfilzomib can be safely administered to subjects with substantial renal impairment (CrCl < 30, including subjects on dialysis) without dose adjustment.^[14] These data indicate that carfilzomib does not exacerbate underlying renal dysfunction, and confirm the "pre-renal" etiology of the BUN/creatinine elevations observed with IV bolus carfilzomib.

In the advanced and refractory multiple myeloma population, the Phase 3 Study PX-171-011 (FOCUS) did not meet the primary objective of demonstrating superiority of carfilzomib monotherapy over the active doublet therapy in the control arm (corticosteroids and optional cyclophosphamide). The median OS with carfilzomib monotherapy was 10.2 months versus 10.0 months for active control. The PFS was similar in both study arms of PX-171-011 (carfilzomib monotherapy 3.7 months versus active control arm 3.3 months, HR = 1.091 [95% CI: 0.843–1.410]).

The efficacy observed in the monotherapy program supported the development of carfilzomib in combination with lenalidomide and low-dose dexamethasone, based on the hypothesis that this combination may result in the ability to deliver optimized proteasome inhibition leading to improved efficacy. Results from the randomized, pivotal, Phase 3 Study PX-171-009 (ASPIRE) demonstrated that carfilzomib in combination with lenalidomide (Revlimid) and low-dose dexamethasone (CRd) in subjects with relapsed multiple myeloma has unprecedented efficacy with an 8.7-month improvement in median PFS when compared with (Revlimid) lenalidomide with low-dose dexamethasone (Rd) (HR = 0.69), and a median PFS of 26.3 months with CRd treatment. Data from Study PX-171-009 (ASPIRE) was submitted to regulatory authorities in the first quarter of 2015 for marketing authorization (currently in review as of January 2015) for the use of carfilzomib in combination with lenalidomide and dexamethasone for the treatment of patients with multiple myeloma who have received at least 1 prior therapy.

1.5 STUDY RATIONALE

Proteasome inhibition affects the levels of numerous cell cycle control proteins, apoptosis, cell adhesion, angiogenesis, and chemoresistance proteins.^[13,14] Carfilzomib and other proteasome inhibitors interrupt cellular pathways integral to the survival of small cell lung cancer,^[15-17] namely the dysregulated apoptotic pathway involving activated nuclear factor-kB (NF-kB).^[18] NF-kB activates the transcription of anti-apoptotic and proliferation genes, mediating tumor cell survival in response to cytotoxic stress and resulting in chemoresistance, a common problem in small cell lung cancer. Carfilzomib prevents proteasomal degradation of IkB, the inhibitor of NF-kB, and also modulates levels of the anti-apoptotic gene Bcl-2 and the tumor suppressor p53. Overexpression of Bcl-2, a key mediator of resistance to apoptosis following chemotherapy, is an important problem in SCLC;^[17] the vast majority of SCLC cases have bcl-2 overexpression, and low levels of bcl-2 and b1-integrin are associated with improved survival in SCLC^[19]. Topoisomerase-1 is thought to cause apoptosis via mechanisms other than NF-kB, adding to the potential synergy of these compounds. In addition, topoisomerase-1 is overexpressed in the majority of subjects with SCLC ^[18] and decreased degradation of this enzyme is expected to lead to further enhancement of this mechanism of apoptosis.

The hypothesis that proteasome inhibition will augment the effect of systemic chemotherapy in solid tumors is not new. In fact, earlier studies using the compound Bortezomib (VELCADE®, Millennium) which only reversibly inhibits the 26S proteasome, with Carboplatin and Gemcitabine showed promising response rates and median survival of 11 months in non-small cell lung cancer (NSCLC)^[20]. Other studies have not shown improvement in response rate or survival with the combination of proteasome inhibitor and Docetaxel or Pemetrexed,^[21] despite substantial preclinical information which would have predicted benefit^[18, 22-24]. The use of Carfilzomib in combination with a topoisomerase inhibitor is expected to differ from previous efforts with other proteasome inhibitors because of its sustained proteasome inhibition and its potential synergy with this class of drugs.

Camptothecins

Camptothecins inhibit topoisomerase I. As a class, camptothecins have shown efficacy in small cell lung cancer in a variety of settings. Several phase II studies demonstrated clinical benefit including the trials of Perez-Soler et al., who showed clinical benefit in 10 out of 32 subjects with extensive stage SCLC in the second line with parenteral topotecan, 1.25 mg/m² daily on Days 1-5 every 21 days^[2] and Ardizzoni et al. who used a higher dose (1.5 mg/m²) but the same schedule, in

101 subjects with relapsed extensive stage disease with median overall survival (6.9 months for sensitive subjects and 4.7 months for refractory subjects (P=0.002).^[25] The pivotal phase III study which led to FDA approval of topotecan in relapsed small cell lung cancer was by Von Pawel et al,^[26] and included 211 subjects with sensitive (> 60 days since prior therapy) relapse and randomized them to either topotecan (107 subjects) daily for 5 days or to cyclophosphamide, doxorubicin, and vincristine (CAV), each given every 21 days. Topotecan showed no significant improvement in the median time to progression (13.3 weeks vs.12.3 weeks, p=0.552) or median survival (25 weeks vs. 24.7 weeks, p=0.795), however, subjects treated with topotecan had improvement in cancer-related symptoms (dyspnea, hoarseness, anorexia, and fatigue) as well as hematologic toxicity.

Another camptothecin, irinotecan, has established activity in small cell lung cancer, as well as nonsmall cell lung cancer, colorectal cancer and ovarian cancer. As a single agent, Negoro and colleagues treated 35 subjects with 100 mg/m² with a response rate of 50% in untreated subjects and 33% in previously treated subjects.^[27] Additional phase II studies of weekly irinotecan by Masuda. et al^[28], demonstrated an objective response rate of 47% and a median survival of 26 weeks (similar to other camptothecins). Le Chevalier and colleagues^[29] used an every 3-week schedule of irinotecan, 350 mg/m², given to 32 chemotherapy-naive SCLC subjects and showed an objective response rate of 16% and a median survival of 4.5 months. Thus, the median survival of camptothecins in the second –line setting in SCLC ranges from 24 to 35 weeks, with those subjects in sensitive relapse having a median survival of 4 to 8 weeks longer than those with refractory relapse. In addition, irinotecan has also been demonstrated to be effective when combined with cisplatin in the front line setting, in extensive stage small cell lung cancer. A Japanese study by Noda, and colleagues demonstrated superiority of this combination when compared to cisplatin and etoposide.^[30] While, these results were not replicated in a Southwest Oncology Group (SWOG) study, the combination is considered an alternative to cisplatin and etoposide in this disease.^[31] The similar efficacy and favorable toxicity of weekly irinotecan delivery justifies its use in the current proposal.

Rationale for Carfilzomib sequencing and combination with topoisomerase inhibitors

Sequencing information for Carfilzomib and other chemotherapeutic drugs is limited. Extrapolating from data using bortezomib, it was shown by several groups that bortezomib sensitized NSCLC and pancreatic cancer cells to gemcitabine, as well as inducing apoptosis in vitro and in vivo.^{[18],[32]}

Sequence dependent enhanced activity was observed by Mortenson and colleagues when bortezomib was given after gemcitabine/carboplatin in NSCLC cell line studies.^[23]

Inactivation of proteasome function allows for increased apoptosis and potentially enhanced antitumor effects in response to treatment with many chemotherapeutic agents. Combination treatment of Carfilzomib with a Topoisomerase-I (Topo-I) inhibitor (e.g., a camptothecin analogue) is anticipated to be at least additive and potentially synergistic as the apoptosis induced by camptothecins in cancer cells may not involve NF- κ B. In addition, proteasome inhibition may interfere with Topo-I degradation, a necessary step in DNA damage repair after exposure to Topo-I poisons. Thus, we hypothesize that Carfilzomib will enhance the anti-tumor efficacy of Irinotecan in relapsed small cell lung cancer.

Rationale for MTD

The phase Ib component of the current trial has completed enrollment. A total of 22 patients were screened with 16 being enrolled. No DLTs were observed at the 20/27 mg/m2 dose level. Two patients experienced DLTs at the 20/45 mg/m2 dose. One event was grade 4 thrombocytopenia lasting \geq 7days and the other was \geq grade 3 diarrhea. Cohort 2 (20/36 mg/m2) included 6 patients, with one patient experiencing a DLT. The MTD was established at the dose level investigated in Cohort 2. The recommended phase II dose has been determined to be: Carfilzomib 20/36 mg/m2 (stepped up dosing) with Irinotecan 125 mg/m2. The phase II component will investigate this combination in patients with relapsed small cell lung cancer.

2 OBJECTIVES

2.1 PRIMARY OBJECTIVE

Phase 1b: Determine maximum tolerated dose (MTD) of Carfilzomib (Day 1, 2, 8, 9, 15, and 16) in combination with Irinotecan (Days 1, 8 and 15) in subjects with relapsed small and non-small cell lung cancer or other irinotecan-sensitive cancers.

Phase II: Assess 6 month survival of relapsed small cell lung cancer in subjects treated with this combination therapy.

2.2 SECONDARY OBJECTIVES:

Phase 1b study: Response rate, safety/tolerability, and biomarker endpoints:

- Carfilzomib proteasome chymotrypsin-like activity in PBMC (LMP7 and b5 activity): relative to the start of irinotecan infusion: pre-dose, 90 min, 2 hr, 5.5 hr on Day 1 of Cycle 1, and pre-carfilzomib infusion on Day 2 of Cycle 1, in all subjects.
- Irinotecan-mediated DNA damage by gamma-H2AX protein expression in PBMC obtained from all subjects relative to the start of irinotecan infusion: pre-dose, 90 min, 2 hr, 5.5 hr on Day 1 of Cycle 1, and pre-carfilzomib infusion on Day 2 of Cycle 1.
- Topoisomerase-I protein expression in PBMC.
- When available, banked tumor tissue for immunohistochemical expression of Topoisomerase-I in all subjects.

**Phase II study**: response rate, safety/tolerability, progression-free survival and biomarker endpoints:

- Carfilzomib proteasome chymotrypsin-like activity in PBMC (LMP7 and b5 activity): relative to the start of irinotecan infusion: pre-dose, 90 min, 2 hr, 5.5 hr on Day 1 of Cycle 1, and pre-carfilzomib infusion on Day 2 of Cycle 1, in 15 subjects in each stratum of Phase II.
- Irinotecan-mediated DNA damage by gamma-H2AX protein expression in PBMC obtained from all subjects relative to the start of irinotecan infusion: pre-dose, 90 min, 2 hr, 5.5 hr on Day 1 of Cycle 1, and pre-carfilzomib infusion on Day 2 of Cycle 1 in 15 subjects in each stratum.

- Topoisomerase-I protein expression in PBMC in **15 subjects in each stratum**
- When available, banked tumor tissue for immunohistochemical expression of Topoisomerase-I in all subjects.

3 EXPERIMENTAL PLAN

3.1 STUDY DESIGN

1. Phase 1b: standard 3+3 design using five dose levels of Carfilzomib. Two dose de-escalations are built into the protocol for safety.

3+3 design	Doses	
	Carfilzomib*	Irinotecan
Cohort -2	$20 mg/m^2$	$75 mg/m^2$
Cohort -1	20 mg/m^2	100 mg/m^2
Cohort 1	$20/27 mg/m^2$	$125 mg/m^2$
Cohort 2	$20/36 mg/m^2$	$125 mg/m^2$
Cohort 3	$20/45 mg/m^2$	$125 mg/m^2$
Cohort 4	$20/56 mg/m^2$	$125 mg/m^2$
Cohort 5	20/70 mg/m ²	$125 mg/m^2$

Table 2. Dose escalation schema

Cycle 1 Day 1 & Day 2 doses are 20 mg/m2. All subsequent days as specified, i.e. 20/27 mg/m2 means Cycle 1 Day 1 & Day 2 doses are 20 mg/m2 and all other days are 27mg/m2.

Phase II: Stratified, single arm trial using MTD of Carfilzomib 20/36 mg/m2 with Irinotecan 125 mg/m2 as established from Phase Ib, in up to 88 small cell lung cancer subjects who have relapsed on a prior platinum regimen.

Stratification for phase II component:. Patients will be accrued in two separate strata; each stratum has its own accrual target and may be closed or open to accrual independently:

- a. Platinum sensitive disease: initial response to platinum-based chemotherapy with progression > 90 days after last treatment.
- b. Platinum refractory disease: No response to platinum-based chemotherapy or progression within 90 days of completing platinum-based therapy. Subjects that progressed during or within one month of completion of platinum-based chemotherapy will be excluded.

3.2 NUMBER OF CENTERS

A minimum of 8 investigative study sites will participate on this trial.

3.3 ESTIMATED STUDY DURATION AND RECRUITMENT

Study duration/timelines: September 2013 – December 2018.

Recruitment: phase 1b: 6 to 9 month recruitment; phase II: 18 to 24 month recruitment.

4 SUBJECT SELECTION

4.1 INCLUSION CRITERIA

Subjects must meet all of the following inclusion criteria to be eligible to enroll in this study. Criteria to the Phase II study are below, criteria specific only to the Phase Ib portion are grayed, .

- 1. Subjects must have histologically or cytologically-confirmed diagnosis of progressive or recurrent malignancy as follows:
 - a. Phase Ib: advanced small or non-small cell lung cancer, or other cancer in which irinotecan therapy has been shown to be effective and for whom no curative therapy exists. Subjects who progressed during or within one month of completing platinumbased chemotherapy will be excluded. Subjects who received primary curative chemoradiation therapy, but who recur within the primary tumor site, previously radiated field or with distant metastases are also allowed to participate. Subjects who have clinical evidence of recurrent cancer do not require a confirmatory biopsy to be eligible for this trial. No limit will be placed on prior regimens received, but prior irinotecan is not allowed.
 - b. Phase II: extensive stage small cell lung cancer with tumor progression or recurrence after treatment with 1 platinum-containing regimen for recurrent or metastatic disease. Subjects who progress during or within one month of completing platinum-based chemotherapy will be excluded. Subjects who received primary curative chemoradiation therapy for limited disease, but who recur within the primary tumor site, previously radiated field or with distant metastases are allowed to participate. Subjects who have clinical evidence of recurrent small cell lung cancer do not require a confirmatory biopsy to be eligible for this trial. Prior irinotecan is *not* allowed.
- 2. Subjects must have measurable disease per RECIST criteria 1.1 (see Appendix B-section 1) performed within 28 days prior to enrollment to treatment. Eligible subjects must be registered within 3 working days prior to initiation of protocol chemotherapy. All other required tests to assess non-measurable disease must be performed within 42 days prior to enrollment to treatment.
- Subjects with known brain metastases are eligible only if he/she has been treated for brain metastasis, are asymptomatic after treatment, have a stable CT or MRI of the brain within 28 days of enrollment to treatment and are not receiving corticosteroid therapy to control symptoms from brain metastasis. Only a non-enzyme inducing anticonvulsant (e.g., Keppra)

will be permitted for those subjects requiring anticonvulsants. (Topical and/or inhaled steroids are allowed.)

- 4. Subjects may have received previous radiation therapy, but it must have been completed at least 21 days prior to enrollment to treatment and the subject should have recovered from all associated toxicities. Measurable disease must be present outside the previous radiation field or a new lesion inside the radiation port must be present. There must be no anticipated need for concurrent radiation therapy during protocol treatment.
- 5. Subjects may have received prior surgery provided that at least 28 days have elapsed since major surgery (thoracic or other major surgeries) and the subject has recovered from all associated toxicities. Subjects must have disease outside of the previous surgical resection area or a new lesion must be present.
- 6. Subjects may have received prior chemotherapy provided that at least 14 days have elapsed from last dose of chemotherapy and the subject has recovered from all associated toxicities.
- Subjects must have a serum creatinine ≤ the institutional upper limit of normal OR a creatinine clearance ≥ 60 cc/min, measured or calculated (Cockcroft-Gault formula), obtained within 14 days prior to enrollment to treatment. Eligible subjects must be registered within 3 working days prior to initiation of protocol chemotherapy.
- 8. Subjects must have adequate hepatic function as documented by a bilirubin ≤ 2 x the institutional upper limit of normal, an alkaline phosphatase ≤ 2 x the institutional upper limit of normal, and an SGOT ≤ 2 x the institutional upper limit of normal all obtained within 14 days prior to enrollment to treatment.
- Subjects must have an ANC ≥ 1,500/µl and a platelet count ≥ 100,000/µl obtained within 14 days prior to enrollment to treatment.
- 10. Subjects must be 18 years of age or older.
- 11. Subjects must have a Zubrod Performance Status as follows (see Appendix B section 4):
 - a. Phase Ib: 0 or 1
 - b. Phase II: 0, 1 or 2
- 12. Subjects must not be pregnant or nursing. Women/men of reproductive potential must have agreed to use an effective contraceptive method (hormonal or barrier method of birth control; abstinence) prior to study entry and for the duration of study participation. Should a woman become pregnant or suspect she is pregnant while participating in this study, she should inform her treating physician immediately.
- 13. Male subjects must agree to practice contraception.

14. All subjects must be informed of the investigational nature of this study and must sign and give written informed consent in accordance with institutional and federal guidelines.

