6.5.1 REQUIRED CONCOMITANT MEDICATIONS

Female subjects of child-bearing potential must agree to use dual methods of contraception for the duration of the study. Male subjects must agree to use a barrier method of contraception for the duration of the study if sexually active with a female of child-bearing potential.

Dexamethasone 8 mg PO/IV will be administered prior to all carfilzomib doses during the first cycle.. A higher dose of dexamethasone may be used per institutional standard. If treatment-related fever, rigors, chills, and/or dyspnea are observed following any dose of carfilzomib after dexamethasone has been discontinued, the subject should receive treatment for infusion reaction per the investigator's institutional standard and dexamethasone (8 mg PO/IV) should be re-instituted and administered prior to all subsequent doses.

All subjects must receive prophylaxis with hydration (see Section 6.1).

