8.2 POST TREATMENT FOLLOW-UP

Phase Ib: All subjects will be followed for 30 days after last treatment and until all drug-associated (possible, probably or definite) toxicities have resolved to Grade 1 or less.

Phase II: All subjects will be followed every 3 months until death or for 2 years after initial registration, or until death, or until study closure whichever occurs first.

9 ADVERSE EVENTS

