Baseline abnormalities will be captured as part of the medical history as described in section 9.1. AEs should be reported from the time of consent through 30 days post-last dose of study drug or initiation of a new anti-cancer therapy, whichever occurs first. In addition, the Investigator should report any AE that may occur after this time period that is believed to have a reasonable possibility of being associated with study drug. If a subject is randomized but discontinues study prior to receiving any study drug, AEs must be reported through the end-of-study visit. AEs which completely resolve and then recur should be recorded as a new AE. For subjects who complete the end of study visit less than 30 days following their last dose of study drug, a follow up of ongoing AEs should be attempted by telephone, and documented in the subject's source. AEs continuing at 30 days post-last dose should have a comment in the source by the Investigator that the event has stabilized or is not expected to improve.

The site Principal Investigator is responsible for evaluating all AEs, obtaining supporting documents, and determining that documentation of the event is adequate.

All Grade 3 and 4 laboratory abnormalities must be recorded as AEs on the CRF. Grade 1 and 2 abnormalities should only be recorded if they require treatment or are otherwise considered clinically significant by the Investigator.

The Principal Investigator may delegate these duties to Subinvestigators and must ensure that these Subinvestigators are qualified to perform these duties under the supervision of the Principal Investigator and that they are listed on the FDA Form 1572.

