- Pulmonary fibrosis which includes symptoms such as- difficulty breathing, including shortness of breath (dyspnea) at rest or with activity or a cough, rapid breathing, feeling like you can't breathe in enough air, or wheezing, which can be signs of lung problems
- •
- Death

Reproductive risks:

Subjects should not become pregnant or father a baby while on this study because the drug in this study could affect an unborn child. It is not known if carfilzomib is transferred to breast milk. Potential subjects who are breastfeeding will be required to discontinue nursing during treatment with carfilzomib and for an additional 30 days following their last treatment with carfilzomib.

Irinotecan may cause fetal harm when administered to pregnant women. Animal studies have revealed evidence of harm to an unborn baby as well as birth defects. Potential risks could include complications such as miscarriage or birth defects. Potential subjects who are breastfeeding will be required to discontinue nursing during treatment with irinotecan and for an additional 30 days following their last treatment with irinotecan.

If you are of childbearing potential, you must use contraception during and for 30 days after the last dose of carfilzomib and irinotecan. Examples of contraceptive methods with a failure rate of less than 1% per year include tubal ligation, male sterilization, hormonal implants, established, proper use of combined oral or injected hormonal contraceptives, and certain intrauterine devices. Alternatively, two methods (e.g., two barrier methods such as a condom and a cervical cap) may be combined to achieve a failure rate of less than 1% per year. Barrier methods must always be supplemented with the use of a spermicide.

Male subjects who have had a vasectomy and testing has shown that there is no sperm present in the semen, the use of birth control method in this study is not required. Otherwise, male subjects must:

- Let their female partner know he is participating in this study.
- Practice abstinence or use a condom during treatment in addition to 30 following final treatment with carfilzomib.

Male subjects must not donate sperm during treat and for an additional 30 days following their last treatment with carfilzomib. To prevent exposure of the unborn child to carfilzomib through semen, the male subject must agree to the use of a condom during vaginal sex.

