9.6 PREGNANCY

It is not known if carfilzomib is harmful to an unborn or breastfed baby. If a subject or their partner becomes pregnant while receiveing this drug, potential risks could include complications such as miscarriage or birth defects. It is not known if carfilzomib is transferred to breast milk. Potential subjects who are breastfeeding will be required to discontinue nursing during treatment with carfilzomib and for an additional 30 days following their last treatment with carfilzomib.

The FDA has assigned Irinotecan to pregnancy category D. It may cause fetal harm when administered to pregnant women. Animal studies have revealed evidence of embryotoxicity and teratogenicity. There are no controlled data in human pregnancy. If the subject or her partner becomes pregnant while receiving this drug, potential risks could include complications such as miscarriage or birth defects. Potential subjects who are breastfeeding will be required to discontinue nursing during treatment with irinotecan and for an additional 30 days following their last treatment with irinotecan.

Pregnant or breastfeeding women and women planning to become pregnant should not participate in this study. If a female subject or the female partner of a male subject is unable to become pregnant because her healthcare provider has determined that she is postmenopausal or she has had her uterus, ovaries, or both fallopian tubes removed, the use of birth control is not required during this study. If a female subject or the female partner of a male subject could become pregnant, she must let her partner know she is in the study. She must agree to discuss acceptable pregnancy prevention methods with the study physician and practice abstinence or use an acceptable method of birth control.

Patient of childbearing potential must use contraception during and for 30 days after the last dose of carfilzomib and irinotecan. Examples of contraceptive methods with a failure rate of < 1% per year include tubal ligation, male sterilization, hormonal implants, established, proper use of combined oral or injected hormonal contraceptives, and certain intrauterine devices. Alternatively, two methods (e.g., two barrier methods such as a condom and a cervical cap) may be combined to achieve a failure rate of < 1% per year. Barrier methods must always be supplemented with the use of a spermicide.

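### For women of child-bearing potential, the contraception rule checked at entry (Section 4.1, item 12) is weaker than the rules in Sections 6.5.1 and 9.6, and those two also differ from each other.

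*Combined protocol and SAP*

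**What the plan says.** Four sections of the combined protocol and SAP set the rule for women of child-bearing potential.

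- **Section 4.1, item 12 (eligibility).** It covers both sexes: anyone able to conceive or father a child "must have agreed to use an effective contraceptive method (hormonal or barrier method of birth control; abstinence) prior to study entry". The commitment lasts as long as they take part. One method is enough, and spermicide is not mentioned. The section opens by stating: "Subjects must meet all of the following inclusion criteria to be eligible to enroll in this study".
- **Section 6.5.1 (concomitant medication).** The rule for women reads: "Female subjects of child-bearing potential must agree to use dual methods of contraception for the duration of the study". Abstinence is not mentioned.
- **Section 9.3.2 (risks of irinotecan).** It gives examples of single methods with failure below 1% per year, then adds: "Alternatively, two methods (e.g., two barrier methods such as a condom and a cervical cap) may be combined" to reach that rate. Any barrier method needs spermicide as well.
- **Section 9.6 (pregnancy).** It repeats the 9.3.2 standard and the spermicide condition. It also says of a woman who could become pregnant: "She must agree to discuss acceptable pregnancy prevention methods with the study physician and practice abstinence or use an acceptable method of birth control". On duration: "Patient of childbearing potential must use contraception during and for 30 days after the last dose of carfilzomib and irinotecan".

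The later part of Section 9.6 describes the birth-control text as specific to carfilzomib. It warns that irinotecan may call for a different method or a longer period, and sends the subject to the study physician. It does not rank the sections.

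**The concern.** Item 12 is what a site ticks before it registers a woman, and it is the weakest of the rules. A site can apply it correctly and register someone whose stated method falls short of two later mandatory sections. The dual-method rule is easy to miss at that stage, because it sits under concomitant medications and not in the eligibility list.

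The stakes are fetal exposure. Section 9.6 places irinotecan in pregnancy category D and says that it may harm a fetus. The Phase II calendar in Section 7 schedules a pregnancy test at screening only, so contraception is the main continuing protection once treatment starts.

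**Working it through.** The documents state no figure on this point, so the check is mainly a comparison of texts.

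**Step 1. Apply each rule to ordinary cases.**

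| Woman's method | 4.1 item 12 | 6.5.1 | 9.6 |
|---|---|---|---|
| One barrier, no spermicide | meets | fails (one method) | fails (no spermicide; not among the listed methods under 1%) |
| One combined oral contraceptive or implant | meets | fails (one method) | meets |
| Abstinence | meets | not provided for | meets |
| Two barriers with spermicide, together under 1% per year | meets | meets | meets |

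The first row shows that item 12 is weaker than both other rules. The second and third rows show that 6.5.1 and 9.6 disagree with each other. The last row shows that all the rules can be met at once.

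**Step 2. Look for a rule of precedence.** None was found. Section 9.6 leaves the choice of method to discussion with the physician, which helps in the individual case but does not tell a site which standard to record.

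**Step 3. Number of women.** Section 11.1 expects about 88 Phase II registrations; Section 1.5 says that Phase Ib enrollment is complete. The share of women of child-bearing potential is not given, so 0% to 5% is assumed:

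- 0%: 88 × 0 = 0
- 1%: 88 × 0.01 = 0.9
- 5%: 88 × 0.05 = 4.4

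**Step 4. Is duration a separate problem?** With six 28-day cycles on schedule and the last carfilzomib dose on day 16 of cycle 6:

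- last dose: 5 × 28 + 16 = day 156
- end of the 30 days in 9.6: 156 + 30 = day 186
- Phase II follow-up limit (Section 8.2: "All subjects will be followed every 3 months until death or for 2 years after initial registration"): 2 × 365 = day 730

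Item 12's period therefore normally outlasts the 30 days. Section 9.3 does foresee early exits ("For subjects who complete the end of study visit less than 30 days following their last dose of study drug"), but 9.6 already imposes the 30 days on those women. Duration adds almost nothing to the point.

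**The case against.** The strongest reply is that no site has to break one rule to keep another. Item 12 can be read as a floor, to which 6.5.1 adds a second method and 9.6 adds spermicide and a physician discussion. That stands. A reader might infer that the protocol has no workable contraception rule, or that a woman admitted on one barrier method will start treatment below standard. The documents support neither inference. Section 6.5.1 is itself a condition to which she must agree, 9.6 requires the discussion with the physician, there is a screening pregnancy test, and both drugs are withheld in pregnancy. The gap lies in what the entry check asks for. It does not show that protection will be absent at the first dose.

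Second, Section 13.2 makes the consent form part of the protocol, and that form was not available here. It may state the method that a woman agrees to. That stands as a limit: the mismatch between the sections is certain, but whether an operative rule appears in the consent form is unknown.

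Third, taking 6.5.1's dual-method line as the default over the fuller text of 9.6 asks for a second method from a woman with, say, an implant or a tubal ligation, both of which 9.6 lists as below 1%. That is fair, and the fix leaves the choice to the sponsor.

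What the reply does not remove is the first row of the table. Item 12 accepts a method that two other mandatory sections reject. The cumulative reading also does not settle abstinence, which 6.5.1 never mentions.

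**Conclusion.** Wrong as written: an internal inconsistency between item 12, Section 6.5.1 and Sections 9.3.2/9.6. It is minor. On the assumed share of 0% to 5% it concerns 0 to about 4 women, and the range includes none. The textual finding does not depend on that assumption. The point has no bearing on sample size, error rates or the primary analysis. It deserves correction because it concerns a safety rule for a regimen containing a category D drug. It covers women only.

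**What to change.** Replace the women's part of item 12 with one rule, and make 6.5.1, 9.3.2 and 9.6 refer to it:

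> Women of child-bearing potential must agree, before study entry, for the duration of study participation and for at least 30 days after the last dose of either drug, to abstinence or to two contraceptive methods used together that achieve a failure rate below 1% per year, with spermicide added to any barrier method.

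If the sponsor confirms that one method listed in 9.6 with failure below 1% per year is sufficient, write that standard into item 12 and amend 6.5.1 to match. Under either choice, item 12 should stop accepting a single barrier method without spermicide.

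Keep the physician discussion in 9.6. Item 12's present sentence covers both sexes, so retain the men's wording when it is split. Check the consent form for the same text.

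The cost is a wording amendment to four sections and that check. No visit, test or procedure is added.
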